1.1 Study Design

This is a non-randomized, open-label Phase I study to assess the pharmacokinetics (PK) of the parent drug 5-aminolevulinic acid (ALA) and its active metabolite protoporphyrin IX (PpIX) during photodynamic therapy applying 3 tubes of BF-200 ALA 10 % gel (Ameluz) in combination with the BF-RhodoLED® lamp in the systemic circulation of diseased individuals presenting with actinic keratosis (AK) on the face/scalp or in the periphery (neck/trunk/extremities) along with subjects' safety/tolerability during and after treatment. The study will be conducted in the US. All study visits and procedures will be conducted at one Phase I unit.

For each subject the following visits are planned:

- a screening visit within 14 days before treatment (Visit 1), at which eligibility of subjects for study participation will be assessed and 1 baseline PK blood sample will be taken
- a baseline/treatment visit, at which eligible subjects will receive PDT with application of 3 tubes of BF-200 ALA, and 14 PK blood samples will be collected, starting 0.5 h prior to BF-200 ALA application and then for up to 10 h afterwards (Visit 2)
- a phone call for safety assessment at 7 (\pm 3) days post PDT (Phone call)
- a further clinic visit, 28 (\pm 7) days after treatment, at which safety and tolerability assessments will be performed (Visit 3)

The primary endpoints of the study are:

- Baseline-adjusted plasma concentrations of ALA for obtaining baseline-adjusted plasma concentration-time curves
- Baseline-adjusted plasma concentrations of PpIX for obtaining baseline-adjusted plasma concentration-time curves

1.2 Objectives

Primary objectives

- Assessment of baseline-adjusted plasma concentration-time curves for ALA after a single PDT treatment applying 3 tubes of BF-200 ALA in conjunction with the BF-RhodoLED® under maximal use conditions in subjects with mild to severe actinic keratosis.
- Assessment of baseline-adjusted plasma concentration-time curves for PpIX after a single PDT treatment applying 3 tubes of BF-200 ALA in conjunction with the BF-RhodoLED® under maximal use conditions in subjects with mild to severe actinic keratosis.

Secondary objectives

- Evaluation of baseline adjusted pharmacokinetic parameters of ALA.
- Evaluation of baseline adjusted pharmacokinetic parameters of PpIX.
- Assessment of safety and tolerability of PDT with BF-200 ALA under maximal use conditions.

Tertiary objectives

- Evaluation of unadjusted plasma concentration-time curve for ALA and evaluation of unadjusted pharmacokinetic parameters of ALA.

- Evaluation of unadjusted plasma concentration-time curve for PpIX and evaluation of unadjusted pharmacokinetic parameters of PpIX.

1.3 Sample Size

Thirty-two (32) subjects will be included in this study, stratified into two groups of 16 subjects each. One of the groups will receive PDT applying 3 tubes of BF-200 ALA in the face/scalp, the other group will receive PDT applying 3 tubes of BF-200 ALA on the neck/trunk/extremities.

A previous PK Phase I study under maximal use conditions in AK subjects with 1 tube of BF-200 ALA (ALA-AK-CT006) had revealed homogeneous baseline-adjusted levels of ALA and PpIX in 12 subjects, with a CV of 53-73% in the key pharmacokinetic parameters after drug application. As statistical evaluation of PK and safety is intended to be performed as descriptive statistics only, no calculation of predictive power is required.

Based on the results of a previous PK study (ALA-AK-CT006), a group size of 12 subjects is considered to be sufficient for proper pharmacokinetic evaluation. In order to compensate for potential drop-outs of subjects as well as potentially higher variability of data due to combined investigation of two treatment areas, stratum size was adapted from 12 to 16 subjects. A drop-out rate of 25% (4 of 16 subjects) was assumed taking into account the complex nature of the study procedures comprising PDT treatment with three tubes and up to two illuminations (simultaneously and if needed), and frequent blood sampling on one single day. For this reason, the sample size of 32 subjects is considered to be adequate for pharmacokinetic evaluation in this PK study.

1.4 Terminology of Treatment Area, Visits and Timepoints

The notation displayed in table 1 and 2 will be used for table, listing and graph (TLG) presentation of treatment areas and visits, respectively.

Table 1: Treatment area

Treatment area/Stratum	Notation used for TLG presentation
face/scalp	Face/scalp
periphery (neck/trunk/extremities)	Periphery

Table 2: Visits and timepoints

Visit	Notation used for TLG presentation
Screening visit (visit 1)	Visit 1
Visit 2/Baseline (PDT) including rescheduled visit	Visit 2
Visit 2 at timepoint -0.5 h in relation to BF-200 ALA application (Baseline for PK)	Visit 2 (-0.5 h)
Visit 2 at timepoint 0.0 h in relation to BF-200 ALA application (Baseline for PK)	Visit 2 (0 h)
Visit 2 at timepoint x* h in relation to BF-200 ALA application:	Visit 2 (x h)
Phone call	Phone call
Visit 3 End of study (EoS)	Visit 3
Unscheduled visit y^	Unscheduled visit y

* x can be any of the following blood sampling timepoints: 0.5, 1, 1.5, 2, 2.5, 3, 3.5, 4, 5, 6, 8, 10

^ y = 1,2,3

2 Endpoints

2.1 Primary Endpoints

The primary endpoints for the study are:

- Baseline-adjusted plasma concentrations of ALA for obtaining baseline-adjusted plasma concentration-time curves
- Baseline-adjusted plasma concentrations of PpIX for obtaining baseline-adjusted plasma concentration-time curves

The analysis of the primary endpoints is described in a separate pharmacokinetics SAP.

2.2 Secondary Endpoints

The following secondary efficacy parameters will be analyzed:

- Baseline-adjusted AUC_{0-t} , baseline-adjusted $AUC_{0-\infty}$, baseline-adjusted C_{max} , T_{max} , $T_{1/2}$, and λ_z for ALA
- Baseline-adjusted AUC_{0-t} , baseline-adjusted $AUC_{0-\infty}$, baseline-adjusted C_{max} , T_{max} , $T_{1/2}$, and λ_z for PpIX
- Frequency and severity of TEAEs / Overall tolerability
- Application site skin reactions in the treatment field(s) during and post PDT
- Application site discomfort during and after illumination reported by the subjects
- Application site pain during PDT on an 11-point Numeric Rating Scale (NRS-11)
- Vital signs
- Safety laboratory
- Physical examinations

All secondary endpoints will be analyzed overall and by stratum (face/scalp or periphery). The analysis of the pharmacokinetics parameters is described in a separate pharmacokinetics SAP.

2.3 Tertiary Endpoints

- Unadjusted plasma concentration-time curve for ALA
- Unadjusted plasma concentration-time curve for PpIX
- Pharmacokinetic parameters of ALA: unadjusted AUC_{0-t} , unadjusted $AUC_{0-\infty}$, unadjusted C_{max} , T_{max} , $T_{1/2}$, and λ_z
- Pharmacokinetic parameters of PpIX: unadjusted AUC_{0-t} , unadjusted $AUC_{0-\infty}$, unadjusted C_{max} , T_{max} , $T_{1/2}$, and λ_z

The analysis of the tertiary endpoints is described in a separate pharmacokinetics SAP.

3 Analysis Sets

3.1 Enrolled set (ENR)

All subjects enrolled in this study i.e. that provided informed consent to participate in the study.

3.2 Enrolled set 2 (ENR2)

All subjects enrolled in this study i.e. that provided informed consent to participate in the study will be included once. Due to COVID-19 implications 2 eligible subjects could not be treated within the visit window. Thus, these subjects were documented as drop-outs and re-screened later. Within enrolled set 2, these subjects will be included with their 2nd screening ID only.

3.3 Treated set (TS)

All subjects that received IMP treatment (including subjects whose PDT treatment was terminated for any reason without illumination). Subjects without any application of IMP will be excluded. If application of any IMP is not certain the subject will be included in the treated set.

3.4 Safety Analysis Set (SAF)

The safety analysis set (SAF) will include all subjects who undergo at least one of the following treatment procedures: preparation of the treatment field(s), application of BF-200 ALA, or illumination. If the conduct of any treatment procedures is not certain, the subject will be included in the SAF.

3.5 Pharmacokinetic Sets

The pharmacokinetic sets are defined for each of the two analytes separately. The pharmacokinetic set per analyte includes all subjects who have at least one evaluable pre-dose and post dose pharmacokinetic sample (i.e., samples taken after the application of BF-200 ALA) for the respective analyte. A post dose sample is regarded evaluable if the plasma concentration is at or above LLOQ. The two pharmacokinetic sets are defined as "PpIX Pharmacokinetic Set" and "ALA Pharmacokinetic Set". These sets will be used for the statistical evaluation of the respective analyte.

The definition of the pharmacokinetic sets is described in detail within a separate pharmacokinetics SAP.

3.6 Assignment of Analysis Sets to Analysis

Pharmacokinetics variables including primary, secondary, and tertiary endpoints are analyzed with pharmacokinetic sets.

If not stated otherwise in the SAP appendix, the following assignment of analysis sets to analysis is used for non-pharmacokinetics variables: The enrolled set and enrolled set 2 are used for the disposition of subjects to analysis sets. The treated set is the analysis set for the summary of subject discontinuation. All other analyses (including all safety parameter) are based on the safety analysis set.

4 Statistical Evaluation

The last non-missing value until start of PDT procedure (preparation of treatment field, application of BF-200 ALA 10 % gel, illumination) will be used as baseline value. This means, assessments of Visit 1, of unscheduled visits, or of Visit 2 (pre-dose) could be used as baseline value.

No replacement of missing values will be done. Laboratory assessments of unscheduled visits will be listed but not included in tables. Thus, if laboratory assessments of a regular visit and of a subsequent unscheduled visit are available, the value of the regular visit will be displayed in tables. Apart from baseline, unscheduled visits will not be used to replace missing data of regular visits. In the unlikely event of missing laboratory assessments of a regular visit and available assessments of a subsequent unscheduled visit, it will be discussed on a case-to-case basis during the DRM whether the assessments of the unscheduled visit will be used for imputation.

The statistical evaluation of pharmacokinetic variables is described in a separate SAP.

All tables will be presented overall and by stratum (face/scalp, periphery). Listings will be sorted by stratum (face/scalp, periphery) and subject. In the unlikely event of actual treatment area differing from planned treatment area, analysis will be stratified by actual treatment area.

All planned analyses are of exploratory nature without any formal statistical hypotheses.

A detailed description of the planned tables, listings and graphs is given in Appendix A (version 1.0).

4.1 Dispositions of Subjects and Analysis Sets

Disposition of subjects and analysis sets

The disposition of subjects and analysis sets, study visits and timepoints, inclusion and exclusion criteria, and the status at study termination will be tabulated.

Details regarding childbearing potential and pregnancy tests will be listed.

4.2 Demographics and Other Covariates

Demographic data

Demographic data (age, sex, race and ethnicity, skin type Fitzpatrick, body height [cm], body weight [kg], body mass index [BMI; calculated: (kg / m²)]) will be tabulated.

Treatment area and assessment of AK lesions

The treatment area (face/scalp or periphery) of subjects, the location of treatment fields (forehead, nose ...), the total area of treatment field [cm²] per subject, the number of treatment fields per subject, the total lesion size of lesions $\geq 4\text{mm}$ [cm²] and the number of AK lesions (stratified by diameter $< 4\text{mm}$ / $\geq 4\text{mm}$) will be tabulated per subject. The size of each AK lesion will be determined by multiplying the largest diameter and the perpendicular diameter. In addition, for lesions $\geq 4\text{mm}$ (target lesions) the diameter (calculated) and severity will be tabulated per lesion.

Medical history and concomitant diseases

The proportion of subjects with relevant medical history or concomitant diseases, with first diagnosis of AK, and with past AK lesions in same region or proximity to treatment field will be tabulated. Medical History and concomitant diseases will not be coded.

Concomitant medication

Concomitant medications (CMs) will be coded by WHO-DD of September 2019. Any medication taken by the subject during the course of the study including over-the-counter medicinal products (dietary supplements, herbal medications, etc.) will be recorded in the eCRF. A CM will be documented once in the eCRF if it is used for several adverse events (AEs) in the same way considering dosing, time frame etc. If a CM is used in different ways for several AEs then it is documented multiple times. For example, if Aspirin is given 1 day for AE1 and AE2, Aspirin is documented once. If Aspirin is given 1 day for AE1 and 2 days for AE2, then Aspirin is documented twice.

Concomitant medications will be tabulated by Anatomic Group (Anatomical therapeutic chemical classification [ATC] level 1), ATC level 4, and preferred name.

Concomitant procedures will be coded by Medical Dictionary for Regulatory Activities (MedDRA) and tabulated by Preferred Term (PT) and System Organ Class (SOC).

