10.2.3 Assessment of target lesions

In this clinical trial, AK lesions of mild to severe intensity (according to Olsen et al., 1991 (37)), of which at least 12 lesions are of a diameter of ≥ 4 mm at screening, will be treated with (field-directed) PDT. AK lesions should be distinguishable; however, no distance restrictions between lesions will be applied.

All lesions within the treatment field(s) have to be counted. For circular or almost circular lesions with a diameter of ≥ 4 mm its location, (e.g. upper arm, forehead), severity and size (diameters) must be documented. For non-circular lesions, the largest diameter and the corresponding perpendicular diameter will be measured and the mean diameter will be calculated and documented.

Furthermore, for smaller actinic lesions (< 4 mm) in the treatment field(s) only the total number has to be documented.

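### Does tabulating lesion size in cm² as the product of two diameters overstate the extent of disease?

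*SAP*

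**What the plan says.** SAP section 4.2, under treatment area and assessment of AK lesions, lists the baseline items to be tabulated per subject. Two of them carry the unit cm²: "the total area of treatment field [cm²] per subject", and "the total lesion size of lesions" of at least 4 mm in diameter. The sentence that follows gives the derivation: "The size of each AK lesion will be determined by multiplying the largest diameter and the perpendicular diameter". The section then adds, for the target lesions, that "the diameter (calculated) and severity will be tabulated per lesion".

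Protocol section 10.2.3 governs what is recorded at the visit. For round or nearly round lesions of at least 4 mm, "severity and size (diameters) must be documented". For the others: "For non-circular lesions, the largest diameter and the corresponding perpendicular diameter will be measured and the mean diameter will be calculated and documented". Below 4 mm the lesions are only counted: "for smaller actinic lesions (< 4 mm) in the treatment field(s) only the total number has to be documented".

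SAP sections 4 and 4.7 leave the detailed layout of tables to the SAP's Appendix A, which is not among the public documents.

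**The concern.** The product of two perpendicular diameters is the area of a rectangle with those sides, not the area of a round or oval lesion. Here it is summed over lesions, given in cm² and placed near a genuine area in cm², so a reader could easily take it for lesion area. The protocol gives no competing definition, because it uses the word size for diameters and defines no lesion measure in cm².

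What would be at stake is the description of the study population. The trial is meant to represent maximal use, and extent of disease is part of that description. A reader who divided total lesion size by field area would get too high a share of diseased skin, and the error would always make disease look more extensive. No other item in SAP section 4.2 gives total lesion extent in cm², so the table offers no direct cross-check.

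**Working it through.** The documents print no lesion-size result, so there is no figure to reproduce. The check is geometric.

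**Inputs.** d1 = largest diameter and d2 = perpendicular diameter (SAP section 4.2). At least 12 lesions of at least 4 mm, in a field of about 60 cm² (Protocol section 6.3). The 10 mm lesion below is an assumed size, for illustration.

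**Factor for round and oval lesions.**
- SAP size = d1 × d2.
- Ellipse area = (π/4) × d1 × d2; a circle is the case d1 = d2.
- Ratio = 4/π = 1.273, an excess of 27.3%, whatever the two diameters. Conversely, the area is π/4 = 0.785 of the product, or 21.5% lower. A sum over such lesions carries the same factor.

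**What that means on the scale of the field.**

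| 12 circular lesions of | Sum of products | Sum of areas | Product, % of 60 cm² | Area, % of 60 cm² |
|---|---|---|---|---|
| 4 mm | 12 × 0.4² = 1.92 cm² | 1.92 × 0.785 = 1.51 cm² | 3.2 | 2.5 |
| 10 mm (assumed) | 12 × 1.0² = 12.00 cm² | 12.00 × 0.785 = 9.42 cm² | 20.0 | 15.7 |

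**Other shapes.** The 27.3% holds only for circles, and for ellipses measured on their axes. Take a rectangle with sides a ≥ b. Its largest diameter is the diagonal, √(a² + b²). The perpendicular chord through the centre is b√(a² + b²)/a. The product is therefore b(a² + b²)/a, against an area of ab, which gives a ratio of 1 + (b/a)². A square gives 2, an excess of 100%, and only a very thin rectangle comes near 1. So no single constant turns the product into an area for irregular lesions.

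**Does anything in the plan use the number?**
- Eligibility (Protocol section 7.3) rests on the count and diameter of lesions, not on a size in cm².
- The analysis sets (Protocol section 14.2, SAP section 3) do not refer to it.
- The pharmacokinetic parameters (Protocol section 14.1; section 10 of the pharmacokinetic SAP) do not use it, and the safety endpoints (SAP section 2.2) do not either.
- No ratio of lesion size to field area is planned in SAP section 4.2.
- All analyses are exploratory, without formal hypotheses (SAP section 4). If both strata have similarly shaped lesions, the factor cancels in any comparison between face/scalp and periphery.

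**The case for a change.** The strongest case for a change is that it would be cheap and the ambiguity is real. A sum in cm² listed close to a field area in cm² invites the reading of lesion area, and round lesions are a fair reference case because the protocol names them. The remedy would be one constant in a program or one row label. That the geometry is right and that a label would do no harm both stand.

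The rest is weaker. SAP section 4.2 keeps two words apart in the same sentence, area for the field and size for the lesions, and the next sentence says exactly how size is formed. The 27.3% appears only if a reader sets that definition aside. The protocol's use of size for diameters is not a contradiction: it concerns what is recorded at the visit, whereas the SAP derives a summary from those measurements and also tabulates the calculated diameter. Multiplying by π/4 would replace a transparent index with a modelled area that is still approximate for the non-circular lesions the protocol provides for.

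One practical point remains. The product cannot be recovered from the mean diameter alone, so both diameters must be kept for non-circular lesions. The protocol has both measured and the SAP formula calls for both, so a programmer following the SAP would use the pair.

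**Conclusion.** This is a matter of labelling, not an arithmetic error, and it calls for no change. The SAP defines a bidimensional product, names it size and gives the formula. Read as an area, the total would be 27.3% too high if lesions are circular or elliptical, and too high by a different amount for other shapes. On a 60 cm² field that is 0.7 percentage points at the eligibility minimum (3.2 − 2.5) and 4.3 points for twelve 10 mm lesions (20.0 − 15.7).

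No endpoint, eligibility decision, analysis set, pharmacokinetic result or planned comparison depends on the number. Lesion counts, diameters and severity are tabulated separately and are unaffected. The conclusion assumes that the published tables keep the SAP's definition in view, and that nobody adds a ratio of lesion size to field area without noting what the numerator is. Appendix A, which could not be checked, may already settle the label; if it does not, whoever lays out the table can name the row as a sum of products of diameters without amending the plan.

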4.3 Study Drug Administration

PDT details (duration of incubation, duration of illumination, number of interruptions) will be displayed using basic statistics. Furthermore, it will be tabulated if preparation of lesions, application of dressing and illumination in all illumination areas was done according to protocol and if all three tubes of IMP were completely used.

4.4 Analysis of Endpoints

4.4.1 Analysis of Primary Endpoints

The analysis of pharmacokinetics is described in a separate SAP.

4.4.2 Analysis of Secondary Endpoints

Frequency and severity of TEAEs / Overall tolerability

AEs will be coded by using the Medical dictionary for regulatory activities (MedDRA). The latest MedDRA version at the day of data base closure will be used. If an AE occurs in multiple treatment fields, it is reported separately for each treatment field within the eCRF. Thus, some AEs are counted repeatedly for the analysis.

Analysis will focus on TEAEs. TEAEs are defined as all AEs or SAEs that occur after lesion preparation at Visit 2, which is at maximum one hour before IMP application (i.e. AE onset date/time \geq date/time of IMP application (Visit 2) – 1h).. If unclear due to incomplete start date/time of AE or IMP application, AEs will be assumed as TEAEs.

TEAEs will be tabulated by system organ class (SOC) and preferred term (PT) (MedDRA). The number of entries, as well as the number and rate of affected subjects will be reported for each treatment area and overall.

TEAEs will also be tabulated by relationship to IMP and/or medical device and by intensity.

TEAEs leading to death, serious TEAEs, TEAEs related to IMP, and TEAEs related to medical device will be presented separately.

TEAEs are considered being related to IMP or medical device, if causal relationship between IMP or medical device and the TEAE is at least possible or relationship assessment is missing.

AEs which occurred before lesion preparation, which is at maximum one hour before IMP application (i.e. AE onset date/time < date/time of IMP application (Visit 2) - 1h) will be listed separately but are not included in any other tables or listings.

Application site skin reactions in the treatment field(s) during and post PDT

The frequency of application site skin reactions for each category (erythema, edema, induration, vesicles, erosion, ulceration, scaling/flaking, scabbing/crusting, discharge/exudate, other) will be presented by intensity and treatment area.

Application site discomfort during and after illumination reported by the subjects

The frequency of application site discomfort for each category (burning, itching, pain, stinging, warmth, other) will be presented by intensity and treatment area.

Application site pain during PDT

Subjects will assess the maximum pain experienced during PDT using an 11-point Numeric Rating Scale (NRS-11) ranging from 0 (no pain at all) to 10 (worst possible pain). Basic statistics for application site pain will be given.

Vital signs

Blood pressure (systolic and diastolic) and heart rate will be analyzed descriptively. Absolute change from baseline to follow-up visits will be descriptively tabulated.

Safety laboratory

Information about clinically significant findings will be displayed using frequency tables. Details regarding laboratory sampling will be listed. In addition, a listing of subjects with clinically significant values will be provided.

Physical examinations

The physical examination will involve head and neck, skin, lymph nodes, thorax including heart and lungs, abdomen, and musculoskeletal, peripheral vascular and nervous system status. Information about clinically significant findings will be displayed using frequency tables. General physical examination will be listed. All clinically significant physical findings will be listed separately.

